8.5 Serious Adverse Events and/or Adverse Events Requiring Discontinuation of Study Drug

Any serious adverse event (SAE) or unexpected AE \geq NCI CTCAE Grade 3 that occurs during this study and up to 30 days after discontinuation of study drug must be reported to the Study Medical Monitor within 24 hours of the Principal Investigator’s awareness of the event, whether or not this reaction is considered to be associated with use of the investigational drug.

In addition, the occurrence of any AE leading to permanent discontinuation of study drug must also be reported to the Sponsor within 24 hours of the Principal Investigator’s awareness of the event.

Serious adverse events must be scanned and emailed to the Sponsor/Study Medical Monitor.

It is expected that the Principal Investigator will provide or arrange appropriate supportive care for the study patient. A patient experiencing a serious adverse event(s) should be followed clinically until the event is resolved, deemed stable or permanent, or the patient starts another treatment for their disease. All telephone and scanned/emailed reports must be followed with a written Serious Adverse Event (SAE) report form within 24 hours of the Principal Investigator's awareness of serious adverse events and nonserious events which required discontinuation of study drug.

The (SAE) report form should be completed and signed by the Principal Investigator, scanned, and sent by email to the Sponsor as described above. The SAE Report Form is distinct and separate from the adverse event form included in the case report form.

Grades for all SAEs and AEs, regardless of whether they trigger expedited reporting or not, must still be captured by the CRF.

8.6 Follow-up of Adverse Events

Adverse events, which are identified on the last scheduled visit, must be recorded on the AE CRF page and reported to the Sponsor according to the procedures outlined in Section 8.4.

Patients with unresolved previously reported adverse events or new adverse events identified on the last scheduled visit should be followed by the Principal Investigator until the events resolve, are deemed stable or permanent, or the patient starts another treatment for their disease. Resolution means the patient has returned to his/her baseline state of health or the Principal Investigator does not expect any further improvement or worsening of the adverse event. The Principal Investigator should continue to report any significant follow-up information to the Sponsor up to the point the event has resolved. Any adverse events reported by the patient to the Principal Investigator which occur after the last scheduled visit, and are determined by the Principal Investigator to be reasonably associated with the use of the study drug or meet the criteria of a reportable adverse event as described above, should be reported to the Sponsor.

Patients withdrawn from the study with an ongoing adverse event must be followed clinically until the event is resolved, deemed stable or permanent, or the patient starts another treatment for their disease. A stable adverse event is defined as an event, which is not expected to change in nature, severity, or frequency. The Principal Investigator should continue to report any significant follow-up information to the Sponsor.

8.7 Patient Deaths

Every effort will be made in the case of patients who die to determine the cause of death. Information regarding a patient who dies more than 30 days after receiving study drug may be recorded on a Death Report Form (no SAE report is required). An SAE report is recorded only if the event leading up to the patient's death began within 30 days of the last administration of study drug.

The Death Report Form is distinct and separate from the adverse event form included in the case report form.

8.8 Reporting Adverse Events to the Regulatory Authorities

The Sponsor will be responsible for reporting adverse events to the FDA as described in 21 CFR Section 312.32 (IND Safety Reports) and to other Regulatory Authorities according to local regulations.

In addition, the Principal Investigator is required by FDA regulations to notify the IRB promptly of all unexpected SAEs occurring at the investigator's study site. The Principal Investigator is also required by FDA regulations to forward the IRB all IND Safety Reports received from the sponsor.

The Sponsor will also report SAEs in compliance with local regulatory requirements.

9. STUDY DRUG MANAGEMENT

9.1 Study Drug

The investigational study drug, alvocidib, will be provided to the Principal Investigator by the Sponsor or designee.

Alvocidib is supplied for parenteral administration as a sterile, nonpyrogenic, injectable, clear pale yellow to yellow-colored, 10 mg/mL solution, which is packaged in glass vials fitted with coated rubber closures crimped with an aluminum seal and light blue plastic cap. Each vial contains 50 mg of alvocidib (calculated with reference to the active moiety). The fill volume has been established to ensure removal of 5 mL. The pH of the solution ranges between 2.7 and 3.3. The solution contains the following excipients: water for injection, glacial acetic acid, and sodium hydroxide (as needed to reach the targeted pH).

Cytarabine and daunorubicin, approved pharmaceutical products, will be provided by commercially available sources.

9.2 Study Drug Dispensing and Accountability

Alvocidib will be provided by the Sponsor to study centers as an investigational drug. The label and package for the drug product will be prepared in accordance with current regulatory requirements. The Investigator or designee will inventory and acknowledge receipt of all shipments of study drugs. The study drugs must be kept in a locked area with access restricted to designated study personnel.

An accurate and current accounting of the dispensing of the study drugs for each patient will be maintained on an ongoing basis by a member of the study site staff in a drug accountability log or equivalent document and will be verified by the sponsor's study monitor. All drug supplies, including unused study drug, must be accounted for. A final inventory of the total amount of drug received at each study site against the amount used and returned must be recorded in the study drug accountability log or an equivalent document. Inventory and dispense records must be readily available for inspection by the study monitor and/or auditor, and open to government inspection at any time. Study drug destruction will be handled by the sites of open/used vials. Unopened study drug vials should be returned to the Sponsor or Courante (CRO) at the end of the study only after full drug accountability has been completed by the study monitor.

9.3 Preparation and Administration

Alvocidib is to be diluted with either 0.9% Sodium Chloride Injection, USP, or 5% Dextrose Injection, USP, prior to infusion, providing solutions of 0.09 to 1.0 mg/mL alvocidib. The diluted solution should be administered according to treatment schedule provided in Section 4.3.2.

Cytarabine (Ara-c), using the 2-gm vial, may be reconstituted with 20 mL of Bacteriostatic Water for Injection with Benzyl Alcohol 0.945% w/v added as preservative. The resulting solution contains 100 mg of cytarabine per mL. Administer according to treatment schedule in Section 4.3.2.

Daunorubicin Hydrochloride Injection, 5 mg/mL, is available as a deep red sterile liquid. The desired dose is withdrawn into a syringe containing 10 mL to 15 mL of 0.9% Sodium Chloride Injection, USP, and then injected into the tubing or side-arm in a rapidly flowing IV infusion of 5% Dextrose Injection, USP, or 0.9% Sodium Chloride Injection, USP. Daunorubicin hydrochloride should not be administered mixed with other drugs or heparin. Administer according to treatment schedule in Section 4.3.2.

Both cytarabine and daunorubicin are approved pharmaceutical products. Complete instructions and training on the proper preparation and administration of all study drugs will be provided to study sites in the Pharmacy Manual.

9.4 Storage at Study Center

- Alvocidib should be stored at USP controlled room temperature (ie, 20°C to 25°C [68°F to 77°F]) with permitted excursions between 2°C to 30°C (36°F to 86°F).
- Cytarabine (Ara-c) should be stored between 15° to 30°C (59° to 86°F).
- Daunorubicin (daunorubicin hydrochloride injection) should be stored at room temperature, 15° to 30°C (59° to 86°F) for up to 24 hours. Contains no preservative. Discard unused portion.

9.5 Compliance

Study drugs will be administered by trained staff at the treatment site(s).

10. RECORD MANAGEMENT

10.1 Data Collection

The Investigator must maintain required records for all study subjects. Case report forms are used to record clinical study data and are an integral part of the study and subsequent reports. Data for this study will be recorded in the subject's source document and into an electronic Case Report Form (eCRF) system that must be kept current to reflect patient status during each part of the study. Patients are not to be identified by name on the eCRF. Appropriately coded identification (site number, patient identification number, and patient initials) should be used.

Electronic CRFs are not to be used as source documents. Investigators must keep accurate separate records (other than the Case Report Forms) of all subjects' visits, being sure to include all pertinent study related information. A statement should be made indicating that the subjects have been enrolled in this clinical study and have provided written Informed Consent. Any adverse events must be thoroughly documented. Results of any diagnostic tests conducted during the study should also be included in the source documentation.

All data should be recorded completely and promptly in the eCRFs as soon after the visit as possible, but no later than 5 days. All queries are to be answered within 3 days of query date.

The Principal Investigator will allow the Sponsor or its representative, or an appropriate representative of the regulatory authorities to inspect study documents (eg, consent forms, drug distribution forms, IRB approval) and pertinent hospital or clinic records for confirmation of data throughout the study period.

10.2 Source Document Maintenance

Source documents are defined as the results of original observations and activities of a clinical investigation. Source documents may include, but are not limited to, hospital medical records, study progress notes, consent forms, computer printouts, laboratory data and recorded data from automated instruments. All source documents produced in this study will be maintained by the Principal Investigator and made available for inspection by representatives of the Sponsor or the Regulatory Authorities. The original signed informed consent form for each participating patient shall be filed with the records kept by the Principal Investigator with a copy filed in the patient's medical records, and a copy given to the patient.

A source document is an original record of information, also known as source data, which is necessary for the reconstruction and evaluation of a clinical trial. The purpose of source documents is to provide proof of a participant's existence, confirm that protocol-related procedures were completed and

conducted per protocol and to verify that data reported in the study CRFs are accurate.

Source documents at a clinical trial site may be maintained in paper or electronic format and typically contain the types of information below. If electronic source documents are used, sponsor and study monitors will be given access to verify study data.

Source documents can include, but are not limited to:

- Notes from clinic physicians, nurses, and other study staff
- Reports of procedures and tests
- Flow sheets, checklists, and worksheets
- Subject diaries, study calendars
- Pharmacy records, accountability logs, shipping receipts
- Study notes or memos to file
- Documented telephone calls, emails, faxes
- Hospital admission forms and discharge summaries
- Sponsor/site-generated study source document templates

Source documents must meet five fundamental principles of data quality (“ALCOA”). They must be:

- **A**tributable – The data originator is identified. If data needs to be amended, the amender is identified.
- **L**egible – The source document must be readable. If handwritten, black or blue ink must be used, never pencil.
- **C**ontemporaneous – The document must be signed and dated when the information is first recorded, with any updates or corrections noted in real time as well.
- **O**riginal – The document must be the first place the information is recorded.
- **A**ccurate – The information must be error-free, and any conflicts with data recorded elsewhere must be reconciled.

10.3 Record Maintenance

The Investigator must retain a comprehensive and centralized filing system of all clinical study-related documentation that is suitable for inspection by the Sponsor and representatives of regulatory authorities.

The Investigator must retain essential study documents (as specified in Section 8 of ICH-GCP and as required by the applicable regulatory requirements) until at least 2 years after the last approval of a marketing application. Patient files and other source data (including copies of protocols, CRFs, original reports of test results, agent-dispensing logs, correspondence, records of informed consent, and other documents pertaining to the conduct of the trial) must be kept for the maximum period of time permitted by the institution.

No trial document will be destroyed without prior written agreement between the Sponsor and the Investigator. Should the Investigator wish to assign the trial records to another party or move them to another location, written agreement must be obtained from the Sponsor.

The Principal Investigator shall take responsibility for maintaining adequate and accurate hard-copy source documents of all observations and data generated during this study, including any data clarification forms (DCF's) received from the Sponsor. Such documentation is subject to inspection by the Sponsor and the FDA or other Regulatory Authorities.

10.4 Study Center File Management

It will be the responsibility of the Principal Investigator to assure that the study file at the center is maintained. The study file for this protocol will contain, but will not be limited to, the information listed below:

- Investigator's Brochure (all versions provided during the study period.)
- Final study protocol.
- Protocol amendments (if applicable).
- Original informed consent form (blank).
- Revised informed consent forms and/or all addenda (if applicable).
- Copy of signed FDA Form(s) 1572
- Curricula Vitae and medical licenses of Principal Investigator and Subinvestigators.
- Financial Disclosure Form of Principal Investigator and Subinvestigators (if applicable).

- DHHS Number for IRB, or other documentation of IRB compliance with FDA regulation (US sites).
- Documentation of IRB/IEC approval of protocol, consent form, any protocol amendments and any consent form revisions.
- Annual IRB/IEC updates and approvals.
- All correspondence between the Principal Investigator, IRB/IEC and Sponsor or Sponsor's representative relating to study conduct.
- Copies of all 7-day and 15-day Safety Reports submitted to the Regulatory Authorities (provided by Sponsor) and IRB/IEC correspondence documenting their submission.
- Laboratory certifications.
- Normal laboratory value ranges for tests required by the protocol for all laboratories that are utilized.
- CRA monitoring log.
- List of signatures and Delegation of Authority for all study personnel
- Drug invoices for both receipt and return of study drug, as well as drug inventory/accountability records.

11. STATISTICAL ANALYSIS

A brief overview of the statistical analysis plan is presented below. Complete details of the planned analysis will be documented in a full Statistical Analysis Plan, which will be finalized before locking the study database.

11.1 Statistical Methods

Statistical analyses will be performed using SAS software version 9.4 or higher. In general, data summaries will be compiled by alvocidib dose level and overall and will include the mean, standard deviation, median, minimum and maximum values for continuous data; the median, 25th and 75th percentiles, minimum and maximum values for time-to-event endpoints; and the number and percentage of patients in each category for categorical data. Pointwise 95% confidence intervals (CI) will also be estimated for the mean (continuous data), median (time-to-event endpoints) or percentage of patients (categorical data).

Baseline value of a characteristic is defined as the last measured value prior to the first dose of alvocidib.

11.2 Sample Size

Given the design and primary objectives of this study, the sample size will be determined by the guidelines governing dose escalation/de-escalation and the identification of DLTs. As a result, the final sample size is not fixed and will not be determined by consideration of inferential analyses conducted via statistical hypothesis testing. It may be anticipated that the study sample size will be up to 40 patients. This is based on observing DLTs in 2 of 3 patients enrolled at the fourth dose level (Cohort 4) and declaring the third dose level as the MTD (3 patients each in the first and second dose levels, 6 patients in the third dose level during dose escalation, 3 patients at the fourth dose level, and an additional 20 patients at the third dose level for confirmation of safety as well as additional safety analysis and feasibility for determining MRD by dual methods [ie, MPFC and NGS] at a central laboratory). However, the actual number of patient enrolled may be slightly more or less depending on the actual pattern and frequency of DLTs.

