Pharmacodynamic Evaluations:	Any evidence of MRD will be determined using standardized techniques (ie, MPFC and NGS) and potential biomarkers including, but not limited to, MCL-1 dependency will also be assessed using bone marrow aspirates and peripheral blood samples.
Study Duration:	The study is expected to take 12-18 months to enroll up to 40 patients.

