4.2.1 Number of Patients

A sufficient number of patients will be screened in order to obtain up to 40 eligible and evaluable patients for dosing. Any patient who withdraws from the study before completing Induction/Reinduction therapy will be replaced unless that patient is withdrawn due to toxicity or has experienced a DLT.

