Open label, multicenter, 3+3 cohort dose escalation of alvocidib for induction therapy combined with 7+3 cytarabine and daunorubicin, followed by optional reinduction with alvocidib combined with 5+2 cytarabine and daunorubicin and/or up to 4 cycles of consolidation therapy with high-dose cytarabine (HiDAC)

Study Populations:

Patients with newly diagnosed, previously untreated AML excluding acute promyelocytic leukemia or core-binding factor AML

Induction Therapy (alvocidib with 7+3):

- Alvocidib on Days 1-3
 - 20-mg/m² IV bolus followed by 30-mg/m² IV infusion over 4 hours, or
 - 30-mg/m² IV bolus followed by 40-mg/m² IV infusion over 4 hours, or
 - 30-mg/m² IV bolus followed by 50-mg/m² IV infusion over 4 hours, or
 - 30-mg/m² IV bolus followed by 60-mg/m² IV infusion over 4 hours
- Cytarabine 100 mg/m²/day continuous IV infusion on Days 5-11
- Daunorubicin 60-mg/m² IV bolus on Days 5-7

Optional Reinduction Therapy (alvocidib with 5+2):

- Alvocidib on Days 1-3 at the same dose used for induction
- Cytarabine 100 mg/m²/day continuous IV infusion on Days 5-9
- Daunorubicin 60-mg/m² IV bolus on Days 5-6

Optional Consolidation Therapy (HiDAC up to 4 cycles):

- Cytarabine 3 g/m² IV q12h on Days 1, 3 and 5 for a total of 6 doses
- A reduced dose of 1.5 g/m² IV q12h was permitted for patients ≥60 years old

Sample Size:

A sufficient number of patients to complete a standard 3+3 cohort dose escalation for up to 4 dose levels plus up to 20 additional patients enrolled at the maximum tolerated dose (MTD) of alvocidib

Analysis Populations:

Intent-to-treat (primary for efficacy), safety, per-protocol

Response Assessments:

Local review of bone marrow and blood test results by the investigator at the study center where patient is enrolled to classify response to treatment following to European LeukemiaNet (ELN) criteria¹

Missing Values:

Missing values will not be replaced by imputed values. Patients who do not supply bone marrow for response assessment are counted among those not achieving remission. Missing time-to-event endpoints will be censored using standard rules detailed below.

Interim Analysis:

No interim analyses. Ongoing review of clinical data performed as required for dose escalation/de-escalation decisions

Efficacy Endpoints:

CR rate (primary endpoint), combined CR rate, combined remission rate, stem cell transplant rate, overall survival, progression-free survival, relapse-free survival, CR duration

Safety Endpoints:

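### The scenario given as the basis for a size of up to 40 adds up to 35, and 40 is not the maximum under the dose-escalation rules either

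*Protocol*

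**What the plan says.** Protocol section 11.2 says that the size is not fixed and is not driven by hypothesis testing. It then gives a figure: "It may be anticipated that the study sample size will be up to 40 patients". The next sentence supplies the basis. It sets the toxicity pattern, two of three patients with a DLT at Cohort 4 and Cohort 3 declared the MTD, and lists the counts: "3 patients each in the first and second dose levels, 6 patients in the third dose level during dose escalation", then "3 patients at the fourth dose level, and an additional 20 patients at the third dose level". The section closes with a caveat that "the actual number of patient enrolled may be slightly more or less depending on the actual pattern and frequency of DLTs".

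The figure appears in two other places. Section 4.2.1 reads "A sufficient number of patients will be screened in order to obtain up to 40 eligible and evaluable patients for dosing", and adds that a patient who withdraws before completing Induction/Reinduction is replaced unless the withdrawal is for toxicity or the patient has had a DLT. The Study Duration row of the Study Summary reads "The study is expected to take 12-18 months to enroll up to 40 patients".

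The rules that generate the total are in section 4.3.3. Table 3 gives 3-6 patients at each of Cohorts -1 and 1 to 4, and its first footnote allows added or intermediate levels. A cohort with one DLT in three receives up to three more patients, the MTD is exceeded at two or more DLTs in 3-6 patients, the level below is filled to at most six, and the expansion is at most 20.

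The SAP gives no total. Its synopsis describes up to four dose levels "plus up to 20 additional patients enrolled at the maximum tolerated dose (MTD) of alvocidib", and its section 5 says that the size is not predetermined.

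**The concern.** The 40 is not offered as a round figure. It is said to follow from a fully itemised scenario, and it does not. A reader who checks the sum cannot tell whether the extra 5 are an allowance for replacements, a rounding, a leftover from another scenario, or a slip. Nor can the figure be read as a worst case, because the rules permit more.

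It is the only overall enrolment total in the documents, and the enrolment period of 12-18 months is stated against it. What is at stake is limited: whether sites, ethics committees and the sponsor have a correct statement of how many patients the described plan uses and how many it could use.

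**Working it through.** **1. The plan's own figure.** Inputs, all from Protocol section 11.2: Cohort 1 = 3, Cohort 2 = 3, Cohort 3 = 6, Cohort 4 = 3, expansion at Cohort 3 = 20.

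3 + 3 + 6 + 3 + 20 = 35, against a stated 40.

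Difference: 40 - 35 = 5, and 5/40 = 12.5%.

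**2. Could an allowance for losses explain it?** Inflating 35 for a 10% loss gives 35/0.90 = 38.9, so 39. Only a loss of 12.5% gives 35/0.875 = 40. No loss rate is stated. Section 4.2.1 also defines the 40 as eligible and evaluable patients, so patients lost and replaced would be added to 40, not contained in it.

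**3. Is 40 the maximum?** Inputs from section 4.3.3 and Table 3: at most six patients per level, at most 20 in the expansion.

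- Cohorts 1 to 4 all at six: 4 × 6 + 20 = 44. One route: Cohorts 1 to 3 each have one DLT in the first three patients and none in the next three; Cohort 4 has one DLT in its first three and the deciding second DLT in its sixth patient; Cohort 3 is then the MTD.
- Cohort -1 also filled: 5 × 6 + 20 = 50. This needs two or more DLTs at each of Cohorts 4, 3, 2 and 1 on the way down, with six patients treated at every level.

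Neither figure includes replaced patients or added dose levels.

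**4. Can the total be exactly 40?** Yes, because the rules say up to 3, 3-6 and up to 20.

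- 3 + 6 + 6 + 5 + 20 = 40: the second DLT at Cohort 4 is seen in the fifth patient, and Cohort 3 is the MTD.
- 3 + 6 + 6 + 6 + 19 = 40: the expansion stops one patient short.

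If cohorts are filled only in blocks of three and the expansion is exactly 20, the totals run 29, 32, 35, 38, 41, 44, 47, 50 and skip 40. The protocol imposes neither condition.

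**5. How often would 40 be exceeded?** The documents give no DLT rates, so these are assumptions: five curves over Cohorts 1 to 4 (5, 10, 15, 20%; 5, 10, 15, 50%; 10, 15, 25, 40%; flat 10%; flat 20%), 5% at Cohort -1, six patients required at the declared MTD, and a full expansion of 20 whenever an MTD is found.

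| Filling of cohorts | Mean total | Total above 40 | Total 44 or more |
|---|---|---|---|
| Blocks of three | 34 to 36 | 9% to 11% | 0.7% to 1.4% |
| Stop at second DLT | 33 to 36 | 4% to 8% | 0.2% to 0.8% |

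Most of the excess is a total of exactly 41. The mean lies close to the 35 of the described scenario.

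**The case against.** The strongest defence is that up to 40 is an upper figure, which a scenario of 35 does not breach, in a section that calls the size not fixed and allows it to be slightly more or less. The SAP also declines to fix a size. Much of this stands. Totals of 41 to 44 arise from the pattern of DLTs, which is what the caveat covers, and they are uncommon under plausible rates. The caveat does not rescue the base case, though: the scenario already fixes the DLT pattern, so that pattern cannot account for a gap between the listed counts and their stated result.

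Two stronger readings are tempting, and neither is supported. A reader might infer that no path through the rules gives 40. That is true only with blocks of three and an expansion of exactly 20; under the actual wording 40 can be reached, as shown above. A reader might also infer that 40 is a hard cap, so that an escalation using 24 patients would cut the expansion to 40 - 24 = 16 and breach the plan. Section 11.2 does not set a hard cap, and the expansion is stated as up to 20 throughout, so 16 would break no rule.

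**Conclusion.** The point holds as an unexplained inconsistency in a stated planning figure. The scenario offered as the basis for 40 gives 35, a shortfall of 5. The rules allow up to 44 with Cohorts 1 to 4, and 50 if de-escalation also fills Cohort -1, in each case with a full expansion and before replaced patients and added levels. So 40 is neither the described case nor the maximum.

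The sum of 35 rests on no assumption. The maxima rest on six patients per level and 20 in the expansion, both from the protocol. The exceedance frequencies rest on assumed DLT rates and show only that passing 40 would be a minority outcome, usually by one patient. The consequence is modest: the analysis is descriptive, and no test, power or precision statement depends on the number.

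**What to change.** In Protocol section 11.2, do one of two things:

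- State 35 for the described scenario and a maximum of 44 (50 if de-escalation reaches Cohort -1) with a full expansion of 20, and say that replaced patients and added dose levels are excluded.
- Keep 40 and state what the extra 5 patients represent. If they are meant as replacements, section 4.2.1 must stop describing all 40 as evaluable.

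Then make section 4.2.1 and the Study Duration row of the Study Summary agree with section 11.2. A minimum is best left out unless its conditions are given: 29 (for example 6 + 3 + 20, with Cohort 1 as the MTD) holds only with a full expansion at a declared MTD, and a smaller expansion, or no MTD at all, gives fewer.

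Leave the expansion as up to 20. Fixing it at 20 would be a design change and is not needed to correct the sum.

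The cost is wording in three places in the protocol. The SAP needs no change, since it states no total. The only drawback is that, under the first option, the published upper figure rises from 40 to 44 or 50.
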